7.7 EXTENT OF EXPOSURE

Treatment exposure will be primarily summarized by the total on-treatment time and has been defined in section 5.4.2 of this TSAP.

7.8 SAFETY ANALYSIS

All safety analyses will be performed on the treated set.

7.8.1 Adverse events

Adverse events will be coded using the Medical Dictionary for Drug Regulatory Activities (MedDRA). Standard BI summary tables and listings will be produced. All adverse events with an onset between start of treatment and end of the residual effect period (REP), a period of 35 days after the last dose of trial medication, will be assigned to the on-treatment period for evaluation.

All treated patients will be included in the safety analysis. In general, safety analyses will be descriptive in nature and will be based on BI standards. No hypothesis testing is planned.

Statistical analysis and reporting of adverse events will concentrate on treatment-emergent adverse events, i.e. all adverse events occurring between start of treatment and end of the residual effect period. Adverse events that start before first drug intake and deteriorate under treatment will also be considered as 'treatment-emergent.'

The analyses of adverse events (AE) will be descriptive in nature. All analyses of AEs will be based on the number of patients with AEs and not on the number of AEs. Frequency of patients with AEs will be tabulated by treatment dose, highest CTCAE grade, system organ class (SoC) and preferred term after coding according to the current version of MedDRA at the database lock. In addition, AEs will be tabulated by preferred terms only. The SoC will be sorted alphabetically. In tables displaying AEs by preferred terms, this will be sorted by descending frequency of AEs in the "Total" BI 905711 group.

Summary tables and listings of AEs, SAEs, related AEs, related SAEs, AEs of special interest, AEs leading to dose reduction, AEs leading to treatment discontinuation and AEs leading to deaths will be provided. In addition the number of DLTs in the MTD period and during the study will be provided.

7.8.2 Laboratory data

The analysis of laboratory data will be descriptively in nature and will follow standard procedures. The analysis of laboratory data will use the same "analyzing treatments" as described for AEs, except for that the baseline laboratory values will be included in the "on treatment" period. Patients having at least one post-baseline laboratory value will be displayed in the descriptive analyses. Patients with missing CTCAE grade at baseline or no baseline value but with post-baseline value will be displayed in the category "Missing CTCAE grade at baseline".

Descriptive statistics, including change from baseline, frequency of patients with transitions relative to the references range, will be provided for laboratory assessments at scheduled visits. Data collected during potential unscheduled laboratory assessments will be listed. No post-study laboratory values will be considered. CTCAE grade for applicable laboratory parameters will be calculated according to CTCAE v5.0. The following outputs will be presented:

- Baseline, last value and difference from baseline
- Worst CTCAE grade experienced during the on-treatment period

- Transitions of the CTCAE grade from baseline to the worst lab values, from baseline to the last lab values, and from the worst to last values during the on-treatment period
- Possible clinically significant laboratory values
- Transitions for laboratory values without CTCAE grade based on reference ranges

Note: For calculating the change in CTCAE grade from baseline, patients with a CTCAE grade of -9 (no CTCAE grade defined) or CTCAE grade of -5 (overlapping reference ranges) will be treated as a CTCAE grade 0 for all analyses. In laboratory listings, the CTCAE grade is displayed as -9 and -5, respectively.

For Uric Acid, Hypokalemia, amylase, bicarbonate, eosinophils, glucose (high direction), INR of prothrombin time, lipase, methemoglobin, sodium (low direction) the CTCAE grade cannot always be assigned by the laboratory parameter itself as two different CTCAE grades have the same laboratory constellation, but are distinguished by additional clinical parameter. In this case a CTCAE grade of -1 will be assigned. These will not be considered for laboratory analyses. In laboratory listings, the CTCAE grade is displayed as -1, respectively.

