3.3.2 Inclusion criteria

- 1. a. Phase Ia (dose escalation only)
 - Histologically or cytologically confirmed, advanced unresectable or metastatic gastrointestinal cancers of following histologies:
 - o Colorectal adenocarcinoma
 - o Gastric adenocarcinoma
 - o Esophageal adenocarcinoma
 - o Pancreatic adenocarcinoma
 - o Cholangiocarcinoma and gallbladder carcinoma
 - o Small intestine adenocarcinoma
 - b. Phase Ib (expansion phase)
 - Histologically or cytologically confirmed, advanced unresectable or metastatic gastrointestinal cancers of following histologies:
 - o Colorectal adenocarcinoma.
 - CDH17 positive pancreatic adenocarcinoma (in tumour tissue as assessed by central testing)
- 2. Patient who has failed all available conventional therapies known to confer clinical benefit for their disease based on local approved standards. For patients with colorectal cancer, prior treatment with regorafenib or TAS-102 is optional.
- 3. a. Phase Ia (dose escalation) only:
 - Patient with either measurable or non-measurable/non-evaluable disease.
 - b. Phase Ia (expanded cohort) and Phase Ib (expansion phase) only:
 - At least one target lesion that can be accurately measured per RECIST v.1.1
- 4. Availability and willingness to provide an archived tumor tissue specimen and undergo tumor biopsy before treatment. Pre-treatment fresh tumor biopsy collections for biomarker analyses are considered optional in phase Ia and mandatory in phase Ib. Only non-

Proprietary confidential information © 2023 Boehringer Ingelheim International GmbH or one or more of its affiliated companies

significant risk procedures per the investigator's judgment will be used to obtain any biopsies specified in this study. In case a fresh tumor biopsy cannot be obtained due to before mentioned reasons an archived tumor tissue specimen obtained within ≤6 months of screening must be submitted. In case the patient undergoes baseline tumor biopsy, an archived tumor tissue specimen must be submitted regardless of the date of collection.

- 5. Adequate hepatic, renal and bone marrow functions as defined by all of the below:
 - a. Total bilirubin (≤ 1.5 x institutional ULN (≤ 3 x institutional ULN for patient with Gilbert's syndrome)
 - b. ALT and AST \leq 2.5 x institutional ULN (\leq 5 x institutional ULN for patients with known liver metastases)

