6. GENERAL ANALYSIS DEFINITIONS

6.1 TREATMENT(S)

This is an open-label, non-randomized, phase I dose escalation and dose expansion study. In phase 1b four CRC cohorts are randomized and a single arm PDAC cohort. For the main analysis the phase 1a and phase 1b data will be pooled together.

The following "analyzing treatment" (Table 6.1:1) will be used for reporting treatment emergent adverse events (AEs) and safety laboratory variables and the timeline criteria "start date \leq onset date of AE < stop date" will be used to determine if an AE will be assigned to be "analyzing treatment" or not. Detailed rule for assigning AEs to these time periods are listed below:

- If the date of informed consent ≤ AE onset date < date/time of the first administration of BI 905711, then the AE is assigned to "Screening";
- If the date/time of the first administration of BI 905711 ≤ AE onset date < min{date of the late administration of BI 905711 + 35 days, DBL date}, then the AE is assigned to "On-treatment";
- If AE onset date ≥ date of the last administration of BI 905711 + 35 days, then the AE is assigned to "Follow-up".

AEs that have onset date during the screening or follow-up periods will be displayed in separate subject listings from those occurred during the on-treatment period. For the ontreatment and follow-up periods, AE frequency tabulations will contain a "total" column, representing all doses of BI 905711. Subject data listings of AEs will not have a "total" column. To justify the MTD determination, DLTs occurring during the MTD evaluation period and the entire on-treatment period will be displayed separately.

Table 6.1:1 Analyzing Treatments

Analyzing Treatment Period	Start Date (including) Stop Date (excluding)		
Screening	Data of informed consent	Date of the first administration of BI 905711	
On-treatment	Date of the first administration of BI 905711	Date of the last administration of BI905711 + 35 days (for discontinued patients); or DBL date (for on-going patients)	
Follow-up	Date of the last administration of BI 905711 + 35 days Note: on-going patients do not have follow-up periods	Date of the last per protocol visit or DBL date, whichever comes first	

MTD evaluation period	Date of the first administration of BI 905711	Date of the second administration of study BI 905711 + 35 days; or DBL date; or the start date of the third treatment cycle, whichever is earlier
-----------------------	--	--

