6.7 BASELINE, TIME WINDOWS AND CALCULATED VISITS

Study days and visits will be labelled according to the CTP's flow chart.

Unless otherwise specified, baseline is defined as the time point closest to and prior to the first administration of study treatment. Note that for some study procedures (e.g. body weight, vital signs, laboratory tests), baseline may be the measurement made on the same day the study treatment was started. In such cases, these measurements will be assumed to have been taken according to the protocol, i.e. prior the first administration of BI 905711.

For laboratory parameters for which not only the examination date but also the sampling time was recorded, examination time should be taken into consideration when defining baseline. That is a laboratory measurement on the same date as the first administration of BI 905711 is considered as baseline if and only if the examination time of the laboratory measurement is before the first administration of BI 905711.

7. PLANNED ANALYSIS.

The following standards for End-Of-Text tables are defined:

- The set of summary statistics for continuous data is: N / Mean / Standard Deviation (StD) / Min / Median / Max. For tables that are provided for endpoints with some extreme data, median, quartiles, and percentiles should be preferred to mean, standard deviation, minimum, and maximum. If not otherwise specified, the abbreviation Pxx should be used for displaying the xxth percentile. Other than the Min and Max, all statistics will be presented to one more decimal place than the raw data.
- Tabulations of frequencies for categorical data will include all possible categories and will display the number of observations in a category as well as the percentage (%) relative to the respective treatment group (unless otherwise specified, all patients in the respective patient set whether they have non-missing values or not). The precision for percentages will be one decimal place. The category "missing" will be displayed only if there are actually missing values.
- For time-to-event analysis tables the set of statistics is: number of patients [N(%)], number of patients with event [N(%)], <time to event> [months] followed by 25th percentile (P25), median, 75th percentile (P75) and number of patients censored [N(%)]. If not specified otherwise the duration as well as the time to event will be displayed in months.

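### SAP 7.8.2 counts the pre-dose baseline as on-treatment, so a patient whose laboratory grade improves throughout is reported at the pre-treatment grade as on-treatment worst

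*SAP*

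**What the plan says.** SAP 7.8.2 takes over the adverse-event analysis periods for laboratory data with one exception: "except for that the baseline laboratory values will be included in the" on-treatment period. Its outputs include "Worst CTCAE grade experienced during the on-treatment period" and the grade transitions from baseline to worst, baseline to last and worst to last during that period. On who is shown, it says: "Patients having at least one post-baseline laboratory value will be displayed in the descriptive analyses".

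In SAP 6.7, "baseline is defined as the time point closest to and prior to the first administration of study treatment". Where a sampling time was recorded, a laboratory value from the first dosing day is baseline "if and only if the examination time of the laboratory measurement is before the first administration of BI 905711". Baseline is thus meant to be a pre-treatment value.

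Adverse events are handled differently. SAP 6.1 assigns an onset before the first administration to the screening period, and SAP 7.8.1 counts an earlier event as treatment-emergent only if it deteriorates under treatment.

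Neither the SAP nor Protocol 7.3.4 limits the worst grade to post-baseline values.

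**The concern.** A table of worst on-treatment grades is read as a description of what happened after dosing. If the baseline value can supply the worst grade, part of the table may describe the patient's state at entry.

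This can realistically occur here. Inclusion criterion 5 in Protocol 3.3.2 admits ALT and AST up to 5 times the "institutional ULN for patients with known liver metastases", haemoglobin from 8.5 g/dL, neutrophils from 1.0 x 10^9/L, and creatinine above 1.5 times ULN when clearance is at least 50 ml/min. Protocol 1.4 names liver injury as an anticipated risk, and Protocol 1.2 lists AST and ALT increases among the most common grade 3 events in Phase Ia. The liver parameters are therefore ones for which a reader will want a clean on-treatment display.

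**Working it through.** The plan states no figure on this point, so there is none to reproduce. The check compares two derivations.

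**Inputs.** Let b be the baseline grade (SAP 6.7), w the worst post-baseline grade and l the last grade, for grades 0 to 4. Only patients with at least one post-baseline value are displayed (SAP 7.8.2), so w and l exist and l <= w.

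**Rules.**
- SAP 7.8.2 as written: worst = max(b, w).
- Post-baseline only: worst = w.

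**Where they differ.** Of the 5 x 5 = 25 possible (b, w) pairs, the rules differ exactly when b > w: 4 + 3 + 2 + 1 = 10 pairs. In the other 15 (w >= b) they agree. The 10 of 25 counts possible combinations; it does not estimate a share of patients.

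**Effect on each output when b > w.**
- Worst-grade table: shows b, a pre-dose grade. With b = 2 and w = 1, it shows 2 instead of 1.
- Baseline to worst: max(b, w) < b is impossible, so 0 of 25 pairs show improvement. The patient falls in the unchanged cell, together with patients whose abnormality persisted.
- Worst to last: l <= w < b, so the table shows a recovery that starts from the pre-treatment value.
- Baseline to last: unaffected, because l is post-baseline.

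**Weight of one patient.** An affected patient moves a percentage at any grade cut-off above w and up to b by 1/n.
- n = 8 (the 0.6, 1.2 and 2.4 mg/kg Phase Ia groups in Protocol 1.2): 1/8 = 12.5 points.
- n = 15 (planned CRC cohort in Phase Ib): 1/15 = 6.7 points.
- SAP 6.1 pools Phases Ia and Ib for the main analysis, which dilutes this at shared doses. With 8 + 15 = 23 patients it is 1/23 = 4.3 points.
- The 3.6 and 4.8 mg/kg levels were not used in Phase Ib. They were planned with at least 4 CRC and up to 4 non-CRC patients, so 12.5 points applies at 8.

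**Number affected.** The documents do not give the share q of patients with b > w for a parameter. For the 48 Phase Ia patients (Protocol 1.2), with q assumed, the expected number is 48q and the chance of at least one is 1 - (1 - q)^48:

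| Assumed q | Expected patients | Chance of at least one |
|---|---|---|
| 2% | 1.0 | 0.621 |
| 5% | 2.4 | 0.915 |
| 10% | 4.8 | 0.994 |
| 20% | 9.6 | > 0.999 |

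**The case against.** The strongest reply is that baseline was placed in the on-treatment period only to keep it with the dose group as the reference for change, since the adverse-event rule would otherwise put it in screening. SAP 7.8.2 elsewhere separates baseline from later values: it requires a post-baseline value for display and has a category for a missing baseline grade. The derivation of worst may also sit in the sponsor's internal laboratory standard, listed in SAP section 8, or in the data guide mentioned in SAP 6.1, neither of which is available here. This reading is plausible, but it is not what the sentence says. The display requirement selects patients; it does not restrict which of their values can be the worst.

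Other parts of the reply stand:
- The baseline-to-worst table separates worsened from unchanged patients, and improvement remains visible in the baseline-to-last table.
- When a patient worsens, max(b, w) equals w, so the error can only overstate the on-treatment grade.
- Safety analysis is descriptive. Clinically relevant laboratory findings are also reported as adverse events (Protocol 5.2.3), which follow the strict pre-dose rule.

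A reader might infer that every patient who enters at grade g or above inflates the on-treatment rate, so that the whole share abnormal at entry is excess. The documents do not support that: a patient who stays at grade g is counted on treatment under either rule. Nor does the sentence create the risk that chance imbalance at entry looks like a dose effect. Persistent abnormalities carry that risk into a post-baseline-only table as well.

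**Conclusion.** The point holds for a limited group. As SAP 7.8.2 is written, patients whose grade is below baseline at every post-dose assessment have their pre-treatment grade reported as the on-treatment worst, and the shifts into and out of the worst value are distorted to match. Each such patient carries 1/n of a dose group. The total effect cannot be stated, because the documents give no rate of improvement and the shares tabulated above are assumptions.

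The conclusion rests on the literal wording and on no other available text overriding it. It concerns the clarity of a descriptive safety table: it does not affect a primary or secondary endpoint, the BLRM or a DLT decision, and it does not conceal toxicity.

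**What to change.** In SAP 7.8.2, state that baseline laboratory values are kept with the treatment group only as the reference for change and as the 'from' side of shifts from baseline. State also that the worst on-treatment grade is derived only from values after the first administration of BI 905711, in the stand-alone table and in the baseline-to-worst and worst-to-last transitions.

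No separate restriction on the last value is needed, because every displayed patient already has a post-baseline value. No extra column for a worst grade above baseline is needed either, since it can be read from the planned baseline-to-worst table.

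The cost is one SAP sentence and one condition in the derivation, with no new data. If the programs already restrict the worst grade to post-dose values, only the sentence changes.

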¹⁰Includes Hematology, Biochemistry, Coagulation, and Urine. Refer to protocol Section 5.2.3 for specific laboratory requirements. Safety lab tests performed during screening do not need to be repeated at Cycle 1 Day 1 if performed within 10 days prior to treatment start and there is no clinical reason to repeat lab tests. During Cycle 1, safety labs should be performed at Day 1, and Day 8. On Cycle 1 Day 1, patients also need to have safety labs performed between 4-6 hours post-dose and repeated at 24 hour timepoint. A patient that experiences an elevated ALT and/or AST value after Cycle 1 Day 1 administration needs to have safety labs performed post-dose after the second and third administrations to assess ALT and AST values. During subsequent cycles, safety labs should be performed within 48 hours prior to each treatment administration as well as at EOT, EOR and at Follow up for PD. Safety lab tests are to be repeated as clinically indicated. At Screening visit, patients are to be tested for hepatitis virus infection which includes hepatitis B surface (HBs) antigen, presence of HBc antibody together with HBV-DNA, and presence of hepatitis C RNA. Results for hepatitis virus infection obtained in routine diagnostics are acceptable if done within 14 days before the informed consent date.

Page 16 of 165

Proprietary confidential information © 2023 Boehringer Ingelheim International GmbH or one or more of its affiliated companies

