⁸To evaluate Exclusion criteria #13, only in cases where the Investigator (or the treating physician or both) suspects cardiac disease with negative effect on the ejection fraction (EF), the EF will be measured during screening using an appropriate method according to local standards to confirm eligibility (e.g., echocardiogram, multigated acquisition scan). A historic measurement of EF no older than 6 months prior to first administration of study drug can be accepted provided that there is clinical evidence that the EF value has not worsened since this measurement in the opinion of the Investigator or of the treating physician or both. Echocardiography (or multigated acquisition scan) may be performed at any time during the study if clinically indicated.

⁹ Dispensing of BI 905711 will be performed via the IRT. Assessment for signs and symptoms of infusion-related reactions and Cytokine Release Syndrome (CRS) is described in Sections 4.1.4.1.1 and 4.1.4.1.2.

¹⁰Includes Hematology, Biochemistry, Coagulation, and Urine. Refer to protocol Section 5.2.3 for specific laboratory requirements. Safety lab tests performed during screening do not need to be repeated at Cycle 1 Day 1 if performed within 10 days prior to treatment start and there is no clinical reason to repeat lab tests. During Cycle 1, safety labs should be performed at Day 1, and Day 8. On Cycle 1 Day 1, patients also need to have safety labs performed between 4-6 hours post-dose and repeated at 24 hour timepoint. A patient that experiences an elevated ALT and/or AST value after Cycle 1 Day 1 administration needs to have safety labs performed post-dose after the second and third administrations to assess ALT and AST values. During subsequent cycles, safety labs should be performed within 48 hours prior to each treatment administration as well as at EOT, EOR and at Follow up for PD. Safety lab tests are to be repeated as clinically indicated. At Screening visit, patients are to be tested for hepatitis virus infection which includes hepatitis B surface (HBs) antigen, presence of HBc antibody together with HBV-DNA, and presence of hepatitis C RNA. Results for hepatitis virus infection obtained in routine diagnostics are acceptable if done within 14 days before the informed consent date.

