4. TREATMENTS

4.1 INVESTIGATIONAL TREATMENTS

4.1.1 Identity of the Investigational Medicinal Products

Table 4.1.1: 1 Test product 1

Substance:	BI 905711
Pharmaceutical formulation:	Powder for Solution for Infusion
Source:	Boehringer Ingelheim Pharma GmbH & Co. KG
Unit strength:	100 mg/vial (10 mg/mL)
Posology:	Single administration every two weeks for a patient enrolled in a biweekly regimen. Single administration every week for 3 weeks on, 1 week off for a patient enrolled in a weekly regimen.
Method and route of administration:	intravenous

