7.3.4 Safety analyses

Adverse events will be coded using the Medical Dictionary for Drug Regulatory Activities (MedDRA). Standard BI summary tables and listings will be produced. All adverse events with an onset between start of treatment and end of the REP, a period of 30 days ($+ \le 5$ days) after the last dose of trial medication, will be assigned to the on-treatment period for evaluation.

All treated patients will be included in the safety analysis. In general, safety analyses will be descriptive in nature and will be based on BI standards. No hypothesis testing is planned.

Statistical analysis and reporting of adverse events will concentrate on treatment-emergent adverse events, i.e. all adverse events occurring between start of treatment and end of the REP. Adverse events that start before first drug intake and deteriorate under treatment will also be considered as 'treatment-emergent'.

Frequency, severity, and causal relationship of adverse events will be tabulated by system organ class and preferred term after coding according to the current version of the Medical Dictionary for Drug Regulatory Activities (MedDRA) at database lock.

Laboratory data will be analyzed both quantitatively as well as qualitatively. The latter will be done via comparison of laboratory data to their reference ranges. Values outside the reference range as well as values defined as clinically relevant will be summarised. Treatment groups will be compared descriptively with regard to distribution parameters as well as with regard to frequency and percentage of patients with abnormal values or clinically relevant abnormal values.

Vital signs, physical examinations, or other safety-relevant data observed at screening, baseline, during the course of the trial and at the end-of-trial evaluation will be assessed with regard to possible changes compared to findings before start of treatment.

Page 101 of 165

Proprietary confidential information © 2023 Boehringer Ingelheim International GmbH or one or more of its affiliated companies

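### From Cycle 3 the weekly Phase Ib arm has three scheduled safety-lab draws per four weeks against two in the biweekly arms, so worst-grade and percentage-abnormal tables modestly favour the biweekly arms at equal true risk

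*SAP*

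**What the plan says.** Protocol 4.1.1 gives the two Phase Ib regimens: "Single administration every two weeks for a patient enrolled in a biweekly regimen", and "Single administration every week for 3 weeks on, 1 week off for a patient enrolled in a weekly regimen". In 14-day cycles the weekly arm is dosed on Days 1 and 8 of odd cycles and Day 1 of even cycles; the biweekly arms are dosed on Day 1 of every cycle (protocol 4.1.2.2).

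Footnote 10 has the same laboratory rule in both full Phase Ib flow charts. For the start of treatment it says "During Cycle 1, safety labs should be performed at Day 1, and Day 8", with extra Cycle 1 Day 1 samples at 4-6 hours and 24 hours. After that, "During subsequent cycles, safety labs should be performed within 48 hours prior to each treatment administration". The weekly chart accordingly marks safety labs on Cycle 3 Day 8 and on Day 8 of later odd cycles. The biweekly chart marks none on those days.

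SAP 7.8.2 lists "Worst CTCAE grade experienced during the on-treatment period" among its outputs, together with grade transitions to the worst value and possibly clinically significant values. It says that descriptive statistics "will be provided for laboratory assessments at scheduled visits" and that unscheduled results are listed. Protocol 7.3.4 adds: "Treatment groups will be compared descriptively with regard to distribution parameters as well as with regard to frequency and percentage of patients with abnormal values". Neither section allows for the number of draws per arm.

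**The concern.** A maximum, or an indicator that a patient was ever abnormal, can only stay the same or rise as draws are added. If one arm is sampled more often, its worst-grade distribution and its percentage abnormal drift upward even when the true risk is equal. The weekly and biweekly 0.6 mg/kg arms are the one contrast of regimens at a fixed dose, so this is where a reader would look for a regimen effect on laboratory safety. Protocol 1.2 describes the drug-related transaminase rises in Phase Ia as transient, and short-lived changes are the kind most affected by how often one looks. At stake is a fair reading of the laboratory tables by regimen in the report.

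**Working it through.** **Plan's own figure.** There is none. The documents give no draw count per arm and no precision for the laboratory comparison, so the counts below come from the flow charts and footnote 10.

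**Scheduled post-dose draws, in days after first dose.**
- Biweekly: 0.2 (4-6 h), 1 (24 h), 7 (Cycle 1 Day 8), then 14, 28, 42, 56 (Day 1 of Cycles 2 to 5).
- Weekly: the same, plus 35 (Cycle 3 Day 8) and 63 (Cycle 5 Day 8).

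From Cycle 3 this is 3 draws against 2 per 4 weeks.

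**Effect at equal true risk.** Let p be the chance that any one draw is abnormal, the same in both arms, and k the number of draws. With independent draws, P(at least one abnormal) = 1 - (1 - p)^k. The documents give no p; 1% to 10% is an assumed range.

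| Horizon | k biweekly / weekly | p = 1% | p = 5% | p = 10% | Difference (points) |
|---|---|---|---|---|---|
| End of Cycle 2 | 4 / 4 | 3.9 / 3.9 | 18.5 / 18.5 | 34.4 / 34.4 | 0 |
| End of Cycle 4 (8 weeks) | 6 / 7 | 5.9 / 6.8 | 26.5 / 30.2 | 46.9 / 52.2 | 0.9 to 5.3 |
| End of Cycle 5 | 7 / 9 | 6.8 / 8.6 | 30.2 / 37.0 | 52.2 / 61.3 | 1.9 to 9.1 |

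Differences are taken before rounding. In an arm of 15, they are 15 × 0.009 = 0.14 to 15 × 0.053 = 0.80 patients at 8 weeks, and 0.28 to 1.36 through Cycle 5. The standard error of a difference between two arms of 15, at a proportion near 40%, is √(2 × 0.4 × 0.6 / 15) = 0.179, about 18 points.

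**Shared draws not counted above.** End-of-treatment (EOT) and end-of-residual-effect (EOR) labs are scheduled in both arms. Two further shared draws multiply each difference by (1 - p)². At p = 10% that is 0.81, giving 5.3 × 0.81 = 4.3 points at 8 weeks and 9.1 × 0.81 = 7.4 through Cycle 5. Correlation between draws within a patient would be expected to reduce the differences further.

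**How many patients are affected.** The first extra draw is 35 days after first dose. Protocol 1.2 gives a Phase Ia median treatment time of 30.5 days overall and 71 days at 0.6 mg/kg. At 30.5 days both arms have 5 draws. If Phase Ib resembled Phase Ia overall, about half the patients would never reach an extra draw.

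**Timing as well as number.** Weekly patients are dosed on Day 8 of odd cycles, so their Day 1 draws in even cycles fall about 7 days after a dose. The matching biweekly draws fall about 14 days after. This already holds at Cycle 2 Day 1, where the draw counts are equal.

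**Dose.** Planned dose per 4 weeks is 3 × 0.6 = 1.8 mg/kg weekly, against 2 × 0.6 = 1.2, 2 × 1.2 = 2.4 and 2 × 2.4 = 4.8 mg/kg biweekly.

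**After restriction to common draws.** Both arms have 4 draws through Cycle 2, 6 through Cycle 4 and 7 through Cycle 5, so the difference due to draw count is 0.

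**The case against.** The case for leaving the plan alone is a fair one.

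- **The decision has gone.** Protocol 1.3 records the end of the development programme and SAP 4 plans an abbreviated report, so use of this comparison in choosing a recommended Phase 2 dose (RP2D) is largely moot. This stands. But SAP 7.8.2 is among the sections revised in the final SAP of 30 November 2023, and it is not withdrawn as the steady-state and dose-proportionality analyses are.
- **Version 7.0 ended the schedule.** The full charts no longer apply. The reduced charts, which start at Cycle 6, leave labs to institutional practice, and results are not entered in the eCRF. This limits the point to data collected before v7.0, which can include the Cycle 3 and Cycle 5 Day 8 draws.
- **By-visit summaries are already planned.** Change from baseline at scheduled visits can be compared at shared visits. That does not equalise worst grade or the percentage ever abnormal.
- **It is descriptive and small.** The difference is well below the sampling error of two arms of 15. This stands, though unlike sampling error it has a known direction.
- **SAP 7.8.2 names no weekly-versus-biweekly contrast.** Treatment labels are left to a separate technical document (SAP 6.1), so the comparison rests on protocol 7.3.4.

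A reader might go further and infer that the sparser schedule misses a quarter of short abnormalities. Assuming onset uniform over Days 0-70 and a 7-day duration, scheduled draws catch 42/70 = 60% on the biweekly chart and 56/70 = 80% on the weekly chart. The arithmetic is right, but the documents do not support it as the size of the effect. They give no duration for any abnormality, and the 70-day horizon leans on the median of eight Phase Ia patients. The calculation also omits EOT and EOR labs and the post-dose ALT/AST samples required after the second and third administrations when a rise follows Cycle 1 Day 1.

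**Conclusion.** The point holds as a modest, correctable imbalance. From Cycle 3 until v7.0, scheduled draws run 3 to 2 per 4 weeks, and the worst-grade, transition-to-worst, clinically-significant and percentage-abnormal outputs take no account of it. At equal true risk the weekly arm tends to look worse by about 1 to 5 percentage points at 8 weeks and 2 to 9 through Cycle 5, or about one patient of 15 at most. This rests on an assumed per-draw probability of 1% to 10%, independent draws, and patients remaining on treatment to those times. Within-patient correlation, shared EOT and EOR labs and early discontinuation would all make it smaller.

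A reader might infer that any excess in the weekly arm is produced by sampling alone. The documents do not support that: each extra draw accompanies an extra dose, and time since last dose differs too, so the tables cannot separate the causes. Nor do they support the inference that an RP2D choice is at risk, since the programme has ended. This is a low-cost improvement to reporting, not a flaw that changes a conclusion.

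**What to change.** In SAP 7.8.2, for the Phase Ib weekly-versus-biweekly comparison, add the worst-grade, transition-to-worst and possibly-clinically-significant tables restricted to draws scheduled in both charts: the shared Cycle 1 draws, pre-dose Day 1 of later cycles, EOT and EOR. Apply the same restriction to the percentage abnormal in protocol 7.3.4. Leave out the conditional post-dose ALT/AST samples, because the second and third administrations fall on different days in the two regimens. Report the number of draws and time on treatment per arm.

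Keep the all-samples tables as the main safety display. Footnote them to say that sampling frequency differs between the weekly and biweekly arms, and that even at common visits weekly draws on Day 1 of even cycles fall about 7 days after a dose rather than 14.

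The cost is one visit filter and one repeated set of tables, with no new data. The restricted tables omit the weekly arm's Day 8 results from Cycle 3 on, which remain in the all-samples tables. They equalise draw count but do not remove the difference in time since last dose.
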